Due to extended proximities and current COVID related guidelines, all discussions will be conducted virtually using Zoom. The initial meeting will be conducted by the PI and RA. The PI will explain the discussion panel's purpose and procedures, including the process, timeline, and expectations. Then, the RA will distribute a handout that briefly describes existing MH services and delivery methods; she will review the Aim 1 findings, including the recommendations and priorities that arose from the groups. After the first meeting, the PI and RA will compile results of the discussion to conceptualize a MH education program. Then, this information will be disseminated to the FR panel for review prior to the next meeting. To allow all individuals to privately agree or disagree with each, a survey will be distributed via Survey Monkey that includes the essential components discussed in the group. Each individual will indicate if they agree or disagree and be able to write additional comments if needed.

The subsequent meetings will aim at reaching consensus on all components of the program. The RA will lead a series of discussions every other week via Zoom, covering the essential components of a MH service model, including (but not limited to) implementation and

Title: Building Partnerships with First Responders to Explore Strategies to Improve Delivery and Access of Mental Health Services

PI: [name], APRN

Institution: University of Arkansas for Medical Sciences

Sponsor: NIH/NIMH

engagement strategies, feasibility, and outcome measures. They will also discuss how to meet the diverse needs within FR populations if differences emerge (e.g. fire vs. ambulance services; urban vs. rural communities) so that the service model will be generalizable to all FRs.

Following each meeting, we will aim for consensus on the key components discussed during the group using the survey method discussed above. This technique will allow us to confirm and document that we have reached consensus.

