When employing a Delphi technique, each round of discussion will involve up to three iterations of deliberations that will seek agreement on essential components of a MH service model. We will plan to have a minimum of 5 meetings: one for introduction, three for discussion and deliberations, and one for final presentation. Using multiple rounds of deliberation, along with a pre-set percentage of agreement, will facilitate a stable and reliable consensus-building process. In the remote chance that consensus is not reached, we will schedule an additional called meeting to additional to further discuss and deliberate

We estimate to have a total of 22-24 participants in the Delphi activities. Upon inviting participants, we will ask them to agree only if they can commit to all meetings, with an allowance of 1 absence, to assure quorum. Specifically, we will use a minimal consensus level of 75% panel agreement for each component.⁶⁰

Compensation

First responders and associated agencies are already strained with the current pandemic, so we want to adequately compensate them for their time. Those that commit to and attend at least 4/5 meetings will receive a \$50 Walmart gift card.

Title: Building Partnerships with First Responders to Explore Strategies to Improve Delivery and Access of Mental Health Services

PI: [name], APRN

Institution: University of Arkansas for Medical Sciences

Sponsor: NIH/NIMH

Ethical Considerations

This study will be conducted in accordance with all applicable government regulations and University of Arkansas for Medical Sciences research policies and procedures. This protocol and any amendments will be submitted and approved by the UAMS Institutional Review Board (IRB) to conduct the study. The PI will carefully monitor study procedures to protect the safety of participants, the quality of the data, and the integrity of the study.

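### The Delphi consensus rule applies only to components; no item or threshold is specified for the assembled service model that Aim 2 is meant to deliver

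*Combined protocol and SAP*

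**What the plan says.** All of this is in the combined protocol and SAP, under Phase 2, Specific Aim 2.

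- **Target.** The aim and its product-development paragraph describe one product: a mental health service model that first responders would accept and that could be put into practice.
- **Ballot.** Under Procedures, "a survey will be distributed via Survey Monkey that includes the essential components discussed in the group". The response is binary with optional comments: "Each individual will indicate if they agree or disagree and be able to write additional comments if needed".
- **Timing and scope.** "The subsequent meetings will aim at reaching consensus on all components of the program", and "Following each meeting, we will aim for consensus on the key components discussed during the group using the survey method discussed above".
- **Meetings.** At least five are planned: "one for introduction, three for discussion and deliberations, and one for final presentation". If consensus is not reached, an additional meeting is to be called.
- **Panel and threshold.** "We estimate to have a total of 22-24 participants in the Delphi activities", and "we will use a minimal consensus level of 75% panel agreement for each component".

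The number of components is not given. Procedures names implementation and engagement strategies, feasibility and outcome measures as an open-ended list.

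**The concern.** The only decision rule acts on parts, while the aim concerns a whole. A panel can reach 75% on each part with a different minority objecting each time, so the share content with every part may be well below 75%. Parts that each look workable may also not be workable together.

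Divided dissent is plausible here. The panel combines administrators with at least 12 first responders from Phase 1, sought from all six regions, and Procedures itself anticipates differences between fire and ambulance services and between urban and rural communities.

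At stake is what Aim 2 can conclude. The survey procedure is said to confirm and document consensus. As described, it would document consensus on components, and a statement that the panel agreed on the model would be an inference. That gap may be hard to close afterwards. Data Handling and Recordkeeping says data are recorded anonymously. If that covers the Delphi surveys, ballots from different meetings could not be linked to count who agreed with everything.

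**Working it through.** The plan gives no derived figure for this stage. The 75% level is a pre-set rule, so there is nothing to reproduce. The check asks what the rule guarantees about agreement with all components at once.

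**Inputs**
- Panel size n = 22, 23 or 24 (protocol estimate).
- Threshold 75% per component (protocol).
- Number of components k: not stated, so treated as an assumption and varied. The topics named can be read as three or four, and the list is open-ended.

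**Step 1: votes needed and dissent allowed per component.** Votes needed = 0.75 × n, rounded up. Dissenters allowed d = n − votes needed.
- n = 22: 16.5, so 17 needed and d = 5.
- n = 23: 17.25, so 18 needed and d = 5.
- n = 24: 18 needed and d = 6.

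**Step 2: guaranteed number agreeing with every component.** If every component passes at the bare minimum and no panelist dissents twice, the number is max(0, n − k × d).

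| Components k | n = 22 | n = 23 | n = 24 |
|---|---|---|---|
| 2 | 22 − 10 = 12 | 23 − 10 = 13 | 24 − 12 = 12 |
| 3 | 22 − 15 = 7 | 23 − 15 = 8 | 24 − 18 = 6 |
| 4 | 22 − 20 = 2 | 23 − 20 = 3 | 24 − 24 = 0 |
| 5 or more | 0 | 0 | 0 |

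For example, with 24 panelists and four components each passing 18 to 6, the dissenters can be four separate groups of six. Every component then passes and nobody agrees with all four.

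**Step 3: a middle case.** If dissent were independent across components and each passed at the bare minimum, the expected number agreeing with all k is n × (votes needed / n)^k. For k = 4:
- n = 22: 22 × (17/22)^4 = 7.8 (36%).
- n = 23: 23 × (18/23)^4 = 8.6 (38%).
- n = 24: 24 × (18/24)^4 = 7.6 (32%).

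**Step 4: the upper end.** If the same people dissent every time and each component just passes, 17 of 22 (77%), 18 of 23 (78%) or 18 of 24 (75%) agree with everything, whatever k is. The 75% level is a minimum, so components may pass by more. If all are unanimous, the figure is 100%.

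**The case against.** The strongest reply is that the text does not rule out a vote on the whole. A survey is to follow each meeting, and the final presentation is one of the meetings, so a survey after it is implied. A reader might infer that the model is never put to a vote. The documents do not support that. They support only that no item or threshold for the assembled model is specified, since the survey is described in terms of components.

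Second, the low counts stack assumptions: four or more components, each passing at the bare minimum, with dissent that never overlaps. The plan works against scattered dissent through private voting with comments, repeated deliberation and the additional called meeting. It may also re-ballot the same components together. This stands, and it is why the counts are bounds and not forecasts.

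Third, agreeing with every part is not endorsing the whole. A panelist may dislike one outcome measure and support the model, or accept each part and doubt the combination. This also stands, but it argues for asking the question directly, because the planned survey cannot separate these cases.

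Fourth, feasibility is itself a listed discussion topic, and Implications and Dissemination of Data places further development and a pilot test of feasibility and acceptability in later work. Both are true. However, the survey described is still on components, and the pilot is a future study for which funding is yet to be sought. Neither supplies a panel judgement on the complete model within this study.

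**Conclusion.** The point holds as a gap in specification, and closing it is a cheap improvement. The component rule alone guarantees that 6-8 of 22-24 panelists agree with everything if there are three components, 0-3 if there are four, and none if there are five or more.

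These figures rest on bare-minimum passes, wholly disjoint dissent and an unstated number of components. With two components, at least 12 or 13 would agree with both.

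Two stronger readings should be avoided. One is that few or no panelists will in fact endorse the model: the documents give no basis for predicting how dissent will fall. The other is that agreement with all components cannot exceed 75%: the threshold is a floor, and the share can reach 100%. What can be said is that the plan as written would not establish where in that range the panel lies, nor whether it endorses the whole.

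**What to change.** In the survey that follows the planned final-presentation meeting, add two agree/disagree items for the whole panel: is the complete model as presented acceptable, and is it feasible? Apply the same 75% level to each, which means 17 of 22, 18 of 23 or 18 of 24.

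State in the protocol that consensus on the model will be claimed only if both items pass. If they do not, use the additional called meeting that the plan already allows. If they still do not pass, report consensus on components only.

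The cost is a short survey on the existing platform and a sentence or two of protocol text. The downside is that the model-level claim may fail although every component passed.
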